9.1 Planned number of subjects

Up to 108 healthy volunteers, excluding replacements: up to 64 in Part A (including 3 optional groups); up to 12 in Part B; and up to 32 in Part C (including 1 optional group).

9.2 Inclusion criteria

The inclusion criteria detailed below should be used to determine eligibility at screening only (unless otherwise specified).

1. Male or female healthy volunteer in good health, as determined by medical history, physical examination, vital signs, 12-lead ECG, and clinical laboratory assessments at the time of screening, as judged by the Investigator.
2. Aged 18–65 years at the time of consent.
3. A body mass index (BMI; Quetelet index) in the range 18.0–30.9 and weight ≥ 50 kg

$$\text{Body Mass Index} = \frac{\text{weight [kg]}}{(\text{height [m]})^2}$$

4. Ability to understand the nature of the trial and any hazards of participating in it. Ability to communicate satisfactorily with the investigator and to participate in, and comply with the requirements of, the entire trial.
5. Willingness to give written consent to participate after reading the information and consent form, and after having the opportunity to discuss the trial with the investigator or their delegate.
6. Willing and able to comply with scheduled visits, treatment plan, laboratory tests, and other study procedures.
7. Agree to follow the contraception requirements of the trial as described in section 11.
8. Agree not to donate blood or blood products during the study and for up to 3 months after the administration of the trial medication.
9. Registered with a General Practitioner (GP) in the UK (Part A only).

10. Willingness to give written consent to have data entered into The Overvolunteering Prevention System.

9.3 Exclusion criteria

The exclusion criteria detailed below should be used to determine eligibility at screening only (unless otherwise specified).

1. Woman who is pregnant or lactating, or pre-menopausal woman who is sexually active and not using a reliable method of contraception (see section 11).
2. Clinically relevant abnormal history, physical findings, ECG, or laboratory values at the pre-trial screening assessment that could interfere with the objectives of the trial or the safety of the volunteer.
3. Presence of acute or chronic illness or history of chronic illness sufficient to invalidate the volunteer's participation in the trial or make it unnecessarily hazardous.
4. History of seizures or at risk of seizure (eg history of significant head trauma).
5. Significant suicidality history or suicidality risk (as assessed by the C-SSRS assessment). Subjects recording "yes" on item four or five of the Suicidal Ideation Section of the C-SSRS with the ideation occurring in the past six months, or "yes" on any item of the Suicidal Behaviour Section.
6. Impaired endocrine, thyroid, hepatic, respiratory or renal function, diabetes mellitus, coronary heart disease, or history of any psychotic mental illness.
7. Surgery (eg stomach bypass) or medical condition that might affect absorption of medicines.
8. History of severe adverse reactions or allergies, or history of an anaphylactic reaction to prescription or non-prescription medication or food (non-active hay-fever is acceptable).
9. Use of a prescription medicine during the 28 days before the first dose of trial medication or use of a non-prescription or over-the-counter medicine (including herbal and nutritional supplements), with the exception of up to 2 g acetaminophen (paracetamol) during the 7 days before and up to 24 h before the first dose of trial medication.
10. COVID-19 symptoms at screening or admission, or positive for COVID-19 testing on admission, as per HMR standard procedures.
11. Subjects with a COVID-19 vaccination within 28 days of their first dose of trial medication, or who are due to receive a dose of a COVID-19 vaccine while participating in the study.

12. Receipt of an investigational product (including prescription medicines) as part of another clinical trial within the 3 months before admission to this study; in the follow-up period of another clinical trial at the time of admission for this study.
13. Presence or history of drug or alcohol abuse, or intake of more than 14 units of alcohol weekly.
14. Habitual, regular use of tobacco and/or nicotine containing products (including e-cigarettes) within 3 months of screening, until the end of the study. Social smokers or vapers may be included in the study (at the discretion of the investigator) provided they can abstain from use of those products from 1 month before the study until the end of the study.
15. Habitual and heavy consumption of caffeinated drinks (> 8 cups of coffee or equivalent per day).
16. Mean blood pressure and pulse rate in supine position at the screening examination outside the ranges: blood pressure 90–140 mm Hg systolic, 40–90 mm Hg diastolic; pulse rate 40–100 beats/min.

One set of repeats in triplicate is permitted if the mean values are borderline (ie values that are within 5 mm Hg for blood pressure or 5 beats/min for pulse rate) or if requested by the investigator. Subjects can be included if the repeat mean value is within range.
17. Possibility that the volunteer will not cooperate with the requirements of the protocol.
18. Evidence of drug abuse on urine testing.
19. Positive test for hepatitis B, hepatitis C or HIV.
20. Loss of more than 400 mL blood during the 3 months before the trial, eg as a blood donor.
21. Objection by GP to volunteer entering trial.
22. AST, ALT, gamma-glutamyl transferase (GGT), or total bilirubin $\geq 1.5 \times$ ULN.

A repeat is allowed on one occasion for determination of eligibility.
23. QT, PR, or QRS value, measured at screening visit on 12-lead ECG, outside of the following ranges: QT value > 450 msec (men) or > 470 msec (women), using Fridericia's formula (QTcF) for correction; PR value outside the range 110–220 msec; QRS value > 120 msec.

TriPLICATE measurements will be made, and a mean value used to determine eligibility. A repeat (in triplicate) is allowed on one occasion for determination of eligibility.
24. Clinically significant findings on 24-hour Holter testing at screening as determined by the Investigator (Part A only).

25. Vegetarian or vegan, or unwilling to eat a high-fat breakfast including bacon (eg for personal or religious reasons) (Part B only).

9.4 Withdrawal of subjects from the trial

9.4.1 *Subject withdrawal*

Subjects are free to withdraw from the trial at any time without giving reasons. Furthermore, the investigator may withdraw a subject for reasons such as intolerance to trial medication, intercurrent illness, need for medication which is contraindicated, significant non-compliance with the requirements of the trial, or withdrawal of consent. The investigator will assess the reasons for withdrawal as far as possible and will fully record the circumstances and medical details.

Subjects will be informed before they agree to take part in the trial that, if they withdraw or are withdrawn:

- the investigator will stop collecting information about them; and
- they can ask the investigator to destroy any identifiable samples taken from them.

The investigator will ask withdrawn subjects to consent to a follow-up examination, to check that they have come to no harm as a result of taking part in the trial.

Provided that the subject agrees, they will undergo, at withdrawal from the trial (or as soon as possible afterwards), the standard medical examination and laboratory tests which they would have undergone had they completed it. The investigator will record in the case report form (CRF) the results of the follow-up examination of withdrawn subjects, if they give their consent for that.

9.4.2 *Individual subject stopping criteria*

A subject who meets any of the following criteria will receive no further doses.

- SAE considered related to study treatment.
- mean QTcF of > 500 msec or increase from baseline of > 60 msec
- $ALT \geq 5 \times ULN$.
- $ALT \geq 3 \times ULN$ and total bilirubin $\geq 2 \times ULN$ or international normalised ratio (INR) of ≥ 1.5 , as per the guidelines for acute liver failure. (If a subject meets that withdrawal criterion, serum bilirubin fractionation should be performed.)
- $ALT \geq 3 \times ULN$ if associated with the appearance or worsening of rash or hepatitis symptoms (fatigue, nausea, vomiting, right upper quadrant pain or tenderness, fever, rash or eosinophilia). Subjects who have $ALT \geq 3 \times ULN$ and $< 5 \times ULN$, and total bilirubin $< 2 \times ULN$, who do not exhibit hepatitis symptoms or rash, can continue in the study (and continue receiving trial

medication) as long as they can be monitored weekly until liver chemistries return to within baseline values.

Subjects who meet the above criteria will be considered discontinued from dosing. However, the investigator may ask the subject to continue their participation in the study, so they can be monitored for safety and PK, or the investigator may withdraw the subject from the trial.

9.4.3 *Replacement of withdrawn subjects*

Withdrawn subjects will be replaced at the discretion of the sponsor and investigator. Subjects withdrawn because of AEs considered possibly related to study treatment (see section 14.2) will not be replaced. Replacements for other withdrawn subjects will receive the treatments intended for the withdrawn subject, from the start of the trial. For subjects in Part B, the sponsor and investigator will decide which sessions the replacement subject will complete.

10 *Treatments*

10.1 *Treatments administered*

In Part A, subjects will receive a single oral dose of BEN8744 or placebo.

In Part B, subjects will receive a single oral dose of BEN8744 on 2 different occasions, separated by a washout of at least 7 days.

In Part C, subjects will receive once or twice-daily oral doses of BEN8744 or placebo for 14 days.

Fasting requirements are described in section 11.

All treatments will be administered orally with approximately 240 mL of water. All treatments will be given in the fasted state in Parts A, and in the fasted or fed state in Part C.

10.2 *Overdose*

Symptoms of overdose of BEN8744 are not yet known. In the case of accidental overdose, subjects should be treated symptomatically as no specific antidote is available.

10.3 *Blinding (Parts A and C only)*

The trial medication will be repackaged and relabelled by the HMR Pharmacy, according to the randomisation schedule. Active and placebo treatments will be labelled such that it is not possible to distinguish between them. If the expiry dates of placebo and active treatment differ, both treatments will be labelled with an expiry

date no later than the earlier of the 2 expiry dates. Each subject's treatment will be given a unique code number, traceable to the batch number of the medication.

The placebo and active treatments for each group will be identical in appearance, and similar in taste and smell. To maintain the blind nature of the trial, the same number of capsules will be given to each subject in a group.

A sealed copy of the randomisation code will be kept in a locked file in the HMR Pharmacy. A copy will also be kept by the bioanalytical laboratory. The investigator will be supplied with sealed envelopes, each one containing the treatment allocation for the subject whose number appears on the outside of the envelope. Those envelopes will be kept in the trial master file, readily accessible to clinical staff. Emergency procedures for revealing medication codes are specified in section 10.4.

The investigators, medical monitor and clinical monitor will remain blinded throughout the trial, unless safety concerns necessitate unblinding (see section 10.4 below).

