8.4 Stopping criteria

8.4.1 *Trial stopping criteria*

The trial will be stopped if either of the following occurs:

- 1 or more SAEs considered to be at least possibly related to study treatment; or
- 2 or more severe or clinically significant adverse events (AEs) that are considered to be at least possibly related to study treatment at any dose level.

In Parts A and C, treatment allocations may be unblinded to aid safety review, provided that the unblinding is appropriately documented. In Part B, all subjects will receive BEN8744.

If, after an internal safety review, it is appropriate to restart the trial, a substantial amendment will be submitted to the MHRA and research ethics committee (REC). The trial will not restart until the amendment has been approved by the MHRA and REC.

8.4.2 *Dose escalation stopping criteria*

A dose level will not be repeated, or exceeded, if:

- the results of safety tests for that dose level give the sponsor or investigator cause for concern,
- the investigator or sponsor considers that dose level to be poorly tolerated.

In addition, a dose level will not be exceeded if:

- plasma concentrations at higher doses in any individual subject are predicted to exceed the exposure threshold (see section 8.5).
- 1 or more Hy's Law cases; Hy's Law is defined as alanine aminotransferase (ALT) and/or aspartate aminotransferase (AST) elevations $\geq 3 \times$ upper limit of normal (ULN) in the presence of a total bilirubin increase $\geq 2 \times$ ULN in the absence of other findings of cholestasis such as a significant increase in alkaline phosphatase (ALP) and without an alternative diagnosis that could explain the increase in ALT/AST and bilirubin.

- 2 or more subjects have a mean QTcF of > 500 msec or increase from baseline of > 60 msec

The trial will be stopped if any criterion in section 8.4.1 is met.

Dosing will be discontinued in an individual subject if any criterion in section 9.4.2 is met.

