8.5.4 Dose escalation Part C (MAD)

Part C may start before the completion of Part A. At a minimum, Part C will not proceed until the SRG has reviewed safety and tolerability (up to 48 h), and PK data (up to 24 h after dosing) from at least 3 groups in Part A, as described in section 8.5.1.

The dose, dosing regimen (once or twice daily), and whether the dose is taken fed or fasted, will be determined by the SRG based on review of available safety, tolerability, and PK data from Parts A and B and previous cohorts in Part C.

Dose selected for Group C1: The first total daily dose (ie, morning plus evening dose, if a twice-daily dosing regimen is chosen) selected for Part C (Group C1) will be the same as, or lower than, a single dose that has been given in Part A without any safety concerns. Additionally, to account for possible accumulation, at the proposed first dose level the predicted C_{max} and AUC_{tau} (at steady state) in any individual subject must not exceed the maximum observed C_{max} and AUC_{inf} achieved so far in Part A.

Doses selected for Groups C2–C3 and optional group C4: It is expected that the dose level tested will increase in each new group. However, the dose will be increased only if, at the new proposed dose level, C_{max} and AUC_{tau} (at steady state) in any individual subject are not predicted to exceed the maximum observed C_{max} and AUC_{inf} achieved following a single dose in Part A that caused no safety concerns.

The daily dose will be increased such that it does not exceed 3.5 times the highest daily dose previously tested in Part C that was safe and well tolerated. Dosing will be discontinued if the criteria in section 8.4.1 are met.

8.5.5 Repeating a dose level or selection of a lower dose level (Parts A and C)

In Parts A and C, the SRG may decide to test a lower dose level of BEN8744, or to repeat a dose level, provided it does not meet the criteria in section 8.4. Such decisions will be made and documented in line with HMR SOPs.

A dose level may be repeated under the following circumstances.

- If it was safe and well tolerated, and resulted in BEN8744 plasma concentrations within the limit (section 8.5.2).

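### Section 9.4.2 stops a subject on ALT only, so a Hy's Law case that section 8.4.2 recognises through AST meets no laboratory threshold for stopping that subject's own doses

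*Combined protocol and SAP*

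**What the plan says.** Protocol section 8.4.2 lists conditions under which a dose level will not be exceeded. One is a single Hy's Law case. Its transaminase limb is "alanine aminotransferase (ALT) and/or aspartate aminotransferase (AST) elevations" of at least 3 × ULN, combined with total bilirubin of at least 2 × ULN. The definition is not purely numeric: other signs of cholestasis must be absent, and the case must be "without an alternative diagnosis that could explain the increase in ALT/AST and bilirubin". The section then passes the individual subject to another rule: "Dosing will be discontinued in an individual subject if any criterion in section 9.4.2 is met".

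Section 9.4.2 has three liver criteria:
- ALT ≥ 5 × ULN;
- "ALT \geq 3 \times ULN$ and total bilirubin $\geq 2 \times ULN", with INR ≥ 1.5 as an alternative to the bilirubin limb;
- ALT ≥ 3 × ULN with rash or hepatitis symptoms.

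AST is in none of them. The remaining criteria in 9.4.2 are a QTcF limit and "SAE considered related to study treatment".

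Section 8.4.1 stops the whole trial on "1 or more SAEs considered to be at least possibly related to study treatment", or on "2 or more severe or clinically significant adverse events (AEs) that are considered to be at least possibly related to study treatment". Section 8.5.4 repeats this for Part C: "Dosing will be discontinued if the criteria in section 8.4.1 are met". Section 9.4.1 lets the investigator withdraw a subject but does not require it.

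**The concern.** A list of individual stopping criteria is meant to give staff on the ward a fixed point at which dosing ends. Here a liver pattern that can count as a Hy's Law case, and so hold back a higher dose for later groups, need not reach any fixed laboratory point for the subject who has it. If that subject still has doses to come, stopping them depends on how the event is classified or on the investigator's discretion. What is at stake is the protection of an individual subject, not the analysis.

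**Working it through.** There is no figure in the plan to reproduce. The check is to run one example through every relevant rule, then count who could be concerned.

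**Example.** AST 4 × ULN, ALT 2.5 × ULN, total bilirubin 2.2 × ULN, INR below 1.5, no cholestasis, no other diagnosis.

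| Rule | Requirement | Met? |
|---|---|---|
| 8.4.2 Hy's Law | ALT and/or AST ≥ 3, bilirubin ≥ 2, both clinical exclusions | Yes, through AST |
| 9.4.2 ALT alone | ALT ≥ 5 | No (2.5) |
| 9.4.2 bilirubin/INR | ALT ≥ 3 with bilirubin ≥ 2, or INR ≥ 1.5 | No (ALT 2.5; INR below 1.5) |
| 9.4.2 symptoms | ALT ≥ 3 with rash or hepatitis symptoms | No (ALT 2.5) |
| 9.4.2 QTcF | QTcF limits | Not relevant |
| 9.4.2 related SAE | Judged serious and related | Depends on judgement |
| 8.4.1 first rule | SAE at least possibly related | Depends on judgement |
| 8.4.1 second rule | Two or more related severe or clinically significant AEs | Depends on grading and on how many AEs are recorded |
| 9.4.1 | Investigator withdraws the subject | Discretionary |

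The bilirubin/INR result is the same whether INR is read as an alternative to bilirubin or as a trigger on its own, because INR is below 1.5 in the example.

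**Who has a dose still to come** (sections 8.1.1 to 8.1.3 and 9.1):
- Part A: one dose each, so its 64 subjects are outside the issue.
- Part B: 2 groups × 6 = 12, all on active drug; 6 without optional Group B2.
- Part C: 4 groups × 8 = 32, of whom 4 × 6 = 24 are on active drug; without optional Group C4, 3 × 8 = 24, of whom 3 × 6 = 18 are on active drug.
- Upper count: 12 + 32 = 44 of 108 (44/108 = 41%), of whom 12 + 24 = 36 are on active drug.
- Without optional groups: 6 + 24 = 30, of whom 6 + 18 = 24 are on active drug.

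These are subjects with a further dose scheduled, not subjects expected to have such a case.

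**Doses that could remain in Part C.** Twice-daily dosing ends with the morning dose of Day 14 (section 12.1.3, note 4), so a subject has 13 × 2 + 1 = 27 doses, against 14 once daily. If the result is known after the morning dose of Day d, the number left is 14 − d once daily, or 27 − (2(d − 1) + 1) = 28 − 2d twice daily. The day is an assumption:
- Day 4: 10 or 20 doses;
- Day 7: 7 or 14 doses;
- Day 10: 4 or 8 doses.

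In Part B, one dose remains after the first session. These are scheduled doses, not a prediction that they would be given.

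**The case against.** The strongest reply is that the two rules do different jobs. Section 8.4.2 governs the next dose level and section 9.4.2 governs the next dose in one subject, so both can be followed at once. Section 9.4.2 never names Hy's Law. In other respects it is the stricter rule: it acts on ALT and bilirubin without waiting to exclude cholestasis or another cause, and it adds INR, ALT-alone and symptom triggers. Using ALT in all three liver criteria could be a deliberate choice. This stands, and it is why the point is incomplete coverage and not an error.

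The second reply is that other rules would probably catch the case. This is largely right:
- Section 14.2 has only two causality categories, and an event with no other diagnosis would very probably be rated possibly related.
- Section 14.1 says that events which might jeopardise the subject should normally be treated as serious. A related SAE stops both the subject and the trial.
- The second rule in 8.4.1 counts events, not subjects. If the AST and bilirubin rises are recorded as two clinically significant AEs, one subject could meet it. Recorded as one AE, the case supplies only one of the two events needed.

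What survives is that each route needs a classification or a decision. Section 14.1 does not list Hy's Law cases as serious, and no route is a laboratory threshold.

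A reader might infer two stronger points. One is that the protocol allows such a subject to continue. It does not: the permission to continue in 9.4.2 requires bilirubin below 2 × ULN, so on this case the text is silent. The other is that a laboratory result alone bars escalation while failing to stop the subject. It does not, because 8.4.2 also needs the two clinical exclusions.

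**Conclusion.** The gap is real but minor. An AST-defined Hy's Law case meets no laboratory stopping criterion in 9.4.2, and its further dosing ends only through a related SAE, the AE count in 8.4.1, or withdrawal under 9.4.1. It could matter for up to 44 subjects (36 on active drug), or 30 (24 on active drug) if the optional groups are not run.

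The event is expected to be rare. Exclusion criterion 22 keeps out subjects with AST, ALT, GGT or bilirubin at or above 1.5 × ULN, and section 6.2.3 reports no clinical pathology effect over 28 days in dogs at up to 10 mg/kg/day. The documents give no rate for such cases, so no probability is offered.

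The conclusion rests on the current wording of 8.4.2 and 9.4.2 and on AST reaching 3 × ULN while ALT does not. If ALT also reaches 3 × ULN, 9.4.2 already stops the subject. The documents do not support a claim that the rules contradict each other, or that endpoints, estimates or escalation decisions are affected.

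**What to change.** In the bilirubin/INR criterion of section 9.4.2, replace ALT ≥ 3 × ULN with ALT and/or AST ≥ 3 × ULN. Leave the ALT ≥ 5 × ULN criterion, the symptom criterion and section 8.4.2 as they are. Pointing 9.4.2 to the Hy's Law definition instead would be weaker, because it brings in the clinical exclusions and so gives no fixed threshold.

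The cost is the wording of one criterion. AST is already in the clinical chemistry panel (Table 11), so no extra test or blood is needed. The downside is that a subject may occasionally be stopped for an AST rise that does not come from the liver. That is limited, because raised bilirubin or INR is still required.

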12.1 Schedules of procedures

12.1.1 *Schedule of procedures (Part A)*

Abbreviations: C-SSRS Columbia-Suicide Severity Rating Scale; ECG = electrocardiogram; FSH = follicle stimulating hormone; FU = follow-up; OAAS/S = Observer's Assessment of Alertness/Sedation scale; PK = pharmacokinetics; VAS = visual analogue scale.

Notes:

1. Screening will be within 28 days before dosing.
2. Follow up will be 7 (± 2) days after discharge.
3. Height at screening only.
4. Subjects will receive a single dose of BEN8744 or placebo in the fasted state, by mouth.
5. Subjects will be resident on the ward from 1 day before their dose (Day -1) until up to 72 h after dosing (Day 4).
6. Full physical examinations will be done at screening. Brief (symptom-directed) physical examinations will be done at all other timepoints.
7. Laboratory safety tests consist of clinical chemistry, haematology, and urinalysis.
8. Pregnancy tests in women of child-bearing potential only. FSH tests in post-menopausal women at screening only.
9. Vital signs consist of: supine systolic and diastolic blood pressure, pulse rate, tympanic temperature and respiratory rate. Triplicate measurements (obtained ≥ 2 min apart) will be made at screening. Single measurements will be made at all other timepoints. Measurements should be made with subjects in a supine position, after resting for 5 min.
10. Triplicate ECG recordings (made ≥ 2 min apart) will be made at screening; single recordings will be done at all other timepoints. Recordings should be made with subjects in a supine position, after resting for 5 min.
11. Subjects will have a 24 h Holter monitor applied during screening and will return the monitor to HMR the following day.
12. Heart rhythm will be monitored continuously (telemetry, 3-lead ECG) from 1 h before until 24 h after dosing.
13. The OAAS/S and VAS will be done immediately before PK blood samples frequently up to 72 h after dosing at the following timepoints: predose and postdose at 0.25, 0.5, 1, 2, 3, 4, 6 and 8 h; on Day 2 (24 h); and on Day 3 (48 h); and on Day 4 (72 h).
14. Blood samples for assay of BEN8744 will be taken on Day 1 at predose and postdose at 0.25, 0.5, 1, 2, 3, 4, 6, 8, 12, and 16 h; on Day 2 (24 and 36 h); on Day 3 (48 h); and on Day 4 (72 h).

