12.4 Methods

Blood collection

Blood will be taken by venepuncture or via a cannula. Cannulae may be inserted under local anaesthesia with lidocaine 0.5%, for withdrawal of venous blood.

After each blood sample, the cannula will be flushed with 3–5 mL normal saline, to keep it patent. In order to minimise dilution of each subsequent blood sample with normal saline, the following procedure will be used: about 1 mL will be drawn via the cannula into the sampling syringe, and discarded. The definitive blood sample will then be taken.

Blood volumes of specific types of samples may vary from those described below, but any change to the sample volumes will not cause the total volume of blood taken during the study to exceed that given in section 12.5.

Samples for laboratory safety tests

Blood will be taken for:

- haematology (2.7 mL in EDTA)
- clinical chemistry, serology, serum pregnancy and/or FSH (4.0 mL in tubes with a gelatin plug)

Blood samples will be collected into 13 × 75 mm tubes. Urine and faeces will be collected in Universal containers. Samples will then be transferred to the laboratory. For logistical reasons, blood, urine, and/or faecal samples may be collected in tubes other than those stated above.

Processing and analysis of samples for laboratory safety tests

Processing of samples will be done by the HMR Analytical Laboratory in accordance with the laboratory's SOPs.

The HMR Analytical Laboratory will do safety tests on blood and urine samples using instruments interfaced to a validated laboratory information management

system (LIMS). Data from analysers that are not interfaced will be entered manually into the LIMS.

Table 11: Laboratory safety tests

Haematology:	Clinical chemistry:
• haemoglobin (Hb)	• urea
• red blood cells (RBC)	• creatinine
• mean corpuscular volume (MCV)	• uric acid
• mean corpuscular haemoglobin (MCH)	• total bilirubin
• mean corpuscular haemoglobin concentration (MCHC)	• total protein
• haematocrit	• albumin
• white blood cells (WBC) and differential (neutrophils, lymphocytes, monocytes, eosinophils, basophils)	• globulin
• platelets	• alkaline phosphatase (ALP)
	• aspartate aminotransferase (AST)
	• alanine aminotransferase (ALT)
	• gamma-glutamyl transpeptidase (GGT)
Urinalysis:	• glucose
• dipstick: protein, blood, ketones, glucose, bilirubin, urobilinogen, leukocyte esterase, specific gravity, nitrites, pH	• phosphate

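### In section 9.4.2 an INR stopping criterion and a sentence allowing continued dosing cover the same subject, and no required test supplies the INR

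*Combined protocol and SAP*

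**What the plan says.** Section 9.4.2 opens with a rule for the whole list: "A subject who meets any of the following criteria will receive no further doses". Two bullets matter here.

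- **Fourth bullet (stop).** The criterion starts from ALT ≥ 3 × ULN together with bilirubin ≥ 2 × ULN, and then adds a further term: "or international normalised ratio (INR) of ≥ 1.5 , as per the guidelines for acute liver failure". Meeting it also calls for bilirubin to be fractionated.
- **Fifth bullet (stop, then a permission).** ALT ≥ 3 × ULN with rash or hepatitis symptoms stops dosing. The bullet then gives a permission for ALT from 3 to below 5 × ULN when bilirubin is below 2 × ULN. It applies to those "who do not exhibit hepatitis symptoms or rash, can continue in the study (and continue receiving trial", meaning the study drug. The permission holds only under a monitoring condition: "as long as they can be monitored weekly until liver chemistries return to within baseline values".

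The section closes by treating subjects who meet the criteria as having stopped dosing.

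On what is measured, section 12 refers the reader to "Table 11: Laboratory safety tests" for the safety variables. That table lists haematology, clinical chemistry, urinalysis and serology. The Part A schedule notes say "Laboratory safety tests consist of clinical chemistry, haematology, and urinalysis", and the Part B and Part C notes say the same.

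**The concern.** A stopping rule for individual subjects has to do two things: give one answer for each subject, and use variables that are in hand when it is applied. The liver rule falls short on both for one type of subject.

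Take ALT 4 × ULN, bilirubin 1 × ULN, INR 1.6 and no symptoms. The fourth bullet stops this subject. The permission in the fifth bullet covers the same subject, because its conditions are ALT, bilirubin and symptoms only. If no INR has been taken, the first sentence cannot be applied and the second can.

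At stake is whether a subject in a first-in-human trial gets further doses, and whether two investigators following the same text would act alike.

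**Working it through.** **1. Is INR supplied by any planned test?** The places where it would appear, in the protocol text available:

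| Place | Content | INR or coagulation |
|---|---|---|
| Section 12.4, Table 11 | Haematology, chemistry, urinalysis, serology | None |
| Section 12.1, schedule notes, Parts A, B and C | Chemistry, haematology, urinalysis | None |
| Section 12.4, tubes for safety tests | One EDTA tube, one gelatin-plug tube | None |
| Section 12.5, Tables 14–16 | Haematology; chemistry/serology/pregnancy/FSH; PK; discard | None |

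INR appears only in 9.4.2 and in the list of abbreviations. The grid of the Part A schedule could not be read, so for Part A this rests on its notes.

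**2. Could a coagulation sample be hidden in the blood budget?** Total = sum over rows of (number of tests × volume per test), from Tables 14–16.

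- Part A: 6 × 2.7 + 6 × 4.0 + 15 × 2.7 + 12 × 1 = 92.7 mL (stated 92.7)
- Part B: 10 × 2.7 + 10 × 4.0 + 30 × 2.7 + 24 × 1 = 172.0 mL (stated 172)
- Part C once daily: 7 × 2.7 + 7 × 4.0 + 31 × 2.7 + 22 × 1 = 152.6 mL (stated 152.6)
- Part C twice daily: 7 × 2.7 + 7 × 4.0 + 37 × 2.7 + 28 × 1 = 174.8 mL (stated 174.8)

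All four totals are reproduced exactly from the listed rows, so no unlisted sample is included.

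**3. Which subjects fall under both sentences?** The inputs to the liver rules were crossed: ALT (< 3, 3 to < 5, ≥ 5 × ULN), bilirubin (< 2, ≥ 2 × ULN), INR (< 1.5, ≥ 1.5) and symptoms or rash (no, yes). That gives 3 × 2 × 2 × 2 = 24 profiles.

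- Stop if ALT ≥ 5; or the fourth bullet is met; or ALT ≥ 3 with symptoms or rash.
- Permission to continue if ALT is 3 to < 5, bilirubin < 2, and no symptoms or rash.

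The fourth bullet joins its terms with an unbracketed *and … or*, so both readings were tried.

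| Reading of the fourth bullet | Profiles under both stop and continue |
|---|---|
| ALT and (bilirubin or INR) | 1 of 24: ALT 3 to < 5, bilirubin < 2, INR ≥ 1.5, no symptoms |
| (ALT and bilirubin) or INR | The same 1 of 24 |

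The overlap does not depend on the reading. For subjects whom the permission covers, INR is the only liver variable that can bring a stop, and the permission does not mention it. These counts are of profiles, not of expected subjects.

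**4. Where would it matter?** Only where a dose is still to come. Part A is single-dose. Part B has a second dose in Session 2, and Part C has 14 days of dosing.

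**The case against.** The best answer is that 9.4.2 already settles the order. Its opening makes any one criterion sufficient, its closing paragraph treats those subjects as having stopped dosing, and the continuation sentence is only permissive. That sentence can be read as explaining what does not meet the fifth bullet, leaving the fourth untouched. This is a fair reading and probably the intended one. But the text does not state it, and an INR that has not been measured cannot trigger a stop on any reading.

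The second answer is that INR can be ordered. Section 12.2 allows extra procedures for subject safety, section 12.3 reserves the investigator's right to do additional safety tests, and section 12.5 allows extra blood. Table 11 is clearly not the limit of testing, since bilirubin fractionation is not in it either. All of this stands. The difference is that fractionation is called for once the criterion is met, whereas INR is needed to decide whether it is met, and nothing requires it at that point.

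The third answer is rarity. Exclusion criteria 6 and 22 remove subjects with impaired hepatic function and those with AST, ALT, GGT or total bilirubin ≥ 1.5 × ULN. ALT ≥ 5 × ULN, ALT ≥ 3 × ULN with bilirubin ≥ 2 × ULN, and ALT ≥ 3 × ULN with symptoms all stop dosing without INR. This stands too, and limits the size of the point.

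**Conclusion.** The point holds as an internal inconsistency with a narrow reach. One liver profile falls under both a stop and a permission to continue, and the variable that separates them is not required to be measured. The event should be rare in screened healthy volunteers; the documents give no rate, and none is estimated here. The practical reach is Part C and Part B before Session 2. The Hy's Law rule for dose escalation in section 8.4.2 does not use INR and is unaffected.

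Two stronger conclusions might be inferred, and the documents do not support them. One is that the protocol lets such a subject be dosed whatever the INR: the continuation sentence is silent on INR, and the framing of 9.4.2 leans towards stopping. The other is that INR would never be seen: it is absent from the planned panel, but an investigator may request it. Nor does the liver rule as a whole depend on INR, since its other inputs are measured or observed.

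The conclusion rests on the protocol text available, and on there being no requirement for INR in the site's own procedures, which were not seen. It takes no position on which clinical rule is right.

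**What to change.** Reconcile the fourth and fifth bullets of 9.4.2 with each other and with Table 11, so that:

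1. the stop and continue sentences cannot both apply to one subject, with the order of precedence stated;
2. the *and … or* in the fourth bullet has a single reading;
3. every variable used by a stopping criterion is available when that criterion is assessed.

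The sponsor decides which clinical rule applies and how the third condition is met.

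The cost is protocol wording. If the sponsor's choice involves an added sample, the documents give no tube volume. Assuming 1.8 to 4.5 mL for one tube, the largest planned total (Part C twice daily) becomes 174.8 + 1.8 = 176.6 mL to 174.8 + 4.5 = 179.3 mL. That slightly exceeds the stated maximum of about 175 mL but uses little of the 50 mL extra allowance in section 12.5 (175 + 50 = 225 mL).
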